6.7. Antiviral Activity Analysis

All antiviral activity analyses described in this section will be based on the FAS and applied for Part B, C, and D only, unless specified otherwise.

6.7.1. Definition of Variables

Selected antiviral activities will be analyzed through the following variables:

- HBV viral parameters (quantitative): HBsAg, HBV RNA, HBcrAg, and HBV DNA (Part D only)
- HBeAg loss: HBeAg changing from positive at baseline to negative at any post-baseline visit (up to Week 8), which will be only applied for participants from Part C and D with qualitative positive HBeAg at baseline.
- HBsAg loss: HBsAg changing from positive (\geq LLOQ) at baseline to negative ($<$ LLOQ) at 2 separate, consecutive, post-baseline visits during the follow-up period (up to Week 8) with at least 2 weeks apart
- Anti-HBs seroconversion: HBsAb changing from negative or missing at baseline to positive (\geq LLOQ) at any post-baseline visit (up to Week 8), which will be only applied for participants with negative or missing Anti-HBs at baseline.

- Anti-HBe seroconversion: HBeAb changing from negative or missing at baseline to positive at any post-baseline visit (up to Week 8), which will be only applied for participants with negative or missing Anti-HBe at baseline.

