In acute resolving infections, the virus is controlled by effective innate and adaptive immune responses that include both cytotoxic T cells capable of directly killing HBV-infected hepatocytes and B cells that produce potent neutralizing antibodies against the virus ([Bertoletti 2016](#); [Li 2016](#); [Maini 2016](#)). In contrast, chronic HBV infection is associated with the inability of the immune system to suppress viral replication and circulation of subviral particles containing the HBV surface antigen (HBsAg). The massive secretion of HBsAg, as well as expression of HBV epitopes on the surface of infected hepatocytes, is thought to contribute to T and B cell dysfunction during chronic HBV infection and to impair the host's ability to clear or control the virus ([Bertoletti 2016](#); [Burton 2018](#); [Maini 2016](#)). The laboratory hallmark of chronic HBV infection is persistence of HBsAg in the blood for greater than 6 months and lack of detectable anti-HBs antibody. Chronic infection is divided into 4 stages based on HBV markers in blood [HBsAg, hepatitis B e-antigen (HBeAg)/anti-HBe antibody, HBV DNA], and liver disease based on biochemical (ALT) and fibrosis markers (noninvasive or based on liver biopsy) ([EASL 2017](#)). Overall, across the various phases of chronic HBV infection, only a minority of patients (less than 1% per year) resolve the disease, as determined by HBsAg seroclearance.

HBV is a DNA virus that infects, replicates, and persists in human hepatocytes ([Protzer 2012](#)). The small viral genome (3.2 kb), consists of partially double-stranded, relaxed-circular DNA (rcDNA) and has 4 open reading frames encoding 7 proteins: HBcAg (HBV core antigen, viral capsid protein), HBeAg, HBV polymerase, PreS1/PreS2/HBsAg (large, medium, and small surface envelope glycoproteins), and HBx (HBV x antigen, regulator of transcription required for the initiation of infection) ([Seeger 2015](#); [Tong 2016](#)).

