2.2. VIR-3434

2.2.1. VIR-3434 Description

VIR-3434 is a half-life extended human monoclonal antibody that binds the antigenic loop present in all forms of the surface envelope protein (small, middle, and large HBsAg). VIR-3434 recognizes all known 10 HBV genotypes (A-J), potently neutralizes HBV virions (5,000x greater neutralizing ability than Hepatitis B Immune Globulin [HBIG]) and reduces serum HBsAg in preclinical animal models. VIR-3434 inhibits viral entry into hepatocytes in vitro. Additional potential effects of VIR-3434 include elimination of HBV infected hepatocytes via antibody dependent cellular cytotoxicity (ADCC)/antibody dependent cellular phagocytosis (ADCP) and induction of HBV-targeting cytotoxic T cells (vaccinal effect). The Fc domain contains mutations that have been engineered to potentially enhance these immune-stimulatory effects and lead to the aforementioned extended half-life.

See the Investigator's Brochure for additional information on VIR-3434.

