Results from a non-GLP PK study in cynomolgus monkeys (PK-3434-0109) was used to develop a linear two-compartment PK model which was further scaled to human using allometry. Human VIR-3434 serum clearance and volume of distribution were predicted to be approximately 65.7 mL/day and 2.43 L, respectively, in the central compartment and 612.7 mL/day and 2.85 L, respectively, in the peripheral compartment. Based on these estimations, terminal elimination half-life of VIR-3434 in humans was predicted to be approximately 58 days. These parameters were used to simulate human PK profiles over the proposed Part A dose range of 90 to 900 mg administered by SC injection and 900 mg and 3,000 mg administered by IV infusion. Additional information is provided in the Investigator’s Brochure.

Table 1: Part A Dose Escalation Plan

Study Part	Cohort	Active:Placebo	Dose (Route)	Frequency of Administration
A	1a	6:2	90 mg (SC)	Once
	2a	6:2	Up to 300 mg (SC)	Once
	3a	6:2	Up to 900 mg (SC)	Once
	4a (Optional)	6:2	Up to 900 mg (IV)	Once
	5a (Optional)	6:2	Up to 3,000 mg (IV)	Once

IV = intravenous; SC = subcutaneous.

Part B: Single Ascending Dose Study in Subjects with Chronic HBV Infection

In Part B, subjects with chronic HBV infection will receive a single dose of study drug. The presence of the therapeutic target of VIR-3434, HBsAg, in subjects with chronic HBV infection alters the potential risks of VIR-3434 administration. Potential risks include immune complex disease due to the formation of antigen-antibody complexes and hepatotoxicity due to elimination of infected hepatocytes via ADCC/ADCP and/or a “vaccinal effect”. To minimize risks to subjects, Part B will be conducted in subjects who are on NRTIs and have HBV DNA < 100 IU/mL at screening, and who have good hepatic reserve and low levels of hepatic inflammation, as determined by lack of significant fibrosis/cirrhosis and ALT $\leq 2 \times$ ULN.

Available non-clinical toxicology and PK/PD data, as well as experience with molecules having similar characteristics, were taken into account when selecting the starting dose and dose escalation scheme for VIR-3434 in subjects with chronic HBV infection. The proposed starting dose of 6 mg (approximately 0.1 mg/kg) is supported by the following rationale:

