6.4. Parts B, C, and D Inclusion Criteria

Each subject must meet all the following inclusion criteria at screening to be eligible for enrollment in the study:

1. Age 18 (or age of legal consent, whichever is older) to 65 years
2. Weight ≥ 40 kg to ≤ 125 kg
3. Chronic HBV infection as defined by the following criteria:
Positive serum HBsAg, HBV DNA, or HBeAg on 2 occasions at least 6 months apart based on previous or current laboratory documentation (any combination of these tests performed 6 months apart is acceptable)
4. Parts B and C only: On NRTI therapy for at least 2 months at the time of screening

5. Parts B and C only: HBV DNA < 100 IU/mL at screening
6. Part D only: HBV DNA \geq 1,000 IU/mL at screening
7. HBsAg > the lower limit of detection
8. Part B only: HBsAg < 3,000 IU/mL at screening
9. Part C only: HBsAg \geq 3,000 IU/mL at screening
10. Part B only: HBeAg-negative at screening
11. Negative anti-HBs at screening
12. Besides chronic infection with HBV, must be in good health, determined from medical history (e.g. chronic conditions such as hypertension, hyperlipidemia, gastroesophageal reflux disease, asthma, anxiety and depression must be well controlled), and no clinically significant findings from physical examination, 12-lead ECG, vital signs, and laboratory values.
13. Female subjects must have a negative pregnancy test or confirmation of postmenopausal status. Post-menopausal status is defined as 12 months with no menses without an alternative medical cause. WOCBP must have a negative blood pregnancy test at screening and a negative urine pregnancy test on Day 1, cannot be breast feeding, and must be willing to use highly effective methods of contraception (Section 6.6) 14 days before study drug administration through 40 weeks after study drug administration. Female subjects must also agree to refrain from egg donation and in vitro fertilization from the time of study drug administration through 40 weeks after study drug administration.

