8.17. Assessment of Screening Viral Parameters, Antiviral Activity, and Resistance Surveillance

During Parts B, C, and D, assessment of screening viral parameters will include: HBsAg, anti-HBs, HBeAg (qualitative), and HBV DNA.

Assessments of antiviral activity performed after screening will include: HBsAg, anti-HBs, HBeAg (qualitative; should only be collected for Parts C and D subjects who are HBeAg qualitative positive at screening), HBeAg (quantitative; should only be collected for Parts C and D subjects who are HBeAg qualitative positive at screening), anti-HBe, HBV RNA, hepatitis B core-related antigen (HBcrAg), and HBV DNA.

Resistance surveillance to monitor for the potential development of resistance to NRTIs or VIR-3434 will be conducted for all subjects who receive study drug. HBV genome sequencing will be attempted in subjects with confirmed HBV DNA breakthrough as defined by having either HBV DNA $\geq 1 \log_{10}$ IU/mL above nadir for 2 consecutive visits or ≥ 500 IU/mL measured at 2 consecutive study visits after having been < 500 IU/mL. HBV genome sequencing will also be attempted in subjects who discontinue early from the study with HBV DNA ≥ 500 IU/mL. As it will not be known at the time of visit if a subject has virologic breakthrough, samples for resistance surveillance will be collected at all study visits noted in the SOA. Samples collected for resistance surveillance may be used to perform additional viral analyses, including viral sequencing.

Details regarding the processing and shipping of the samples are provided in the Laboratory Manual.

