10.6. Antiviral Activity Analysis

For Parts B, C, and D, selected data relating to the antiviral activity of VIR-3434, such as HBsAg, anti-HBs, HBeAg, anti-HBe, HBV RNA, HBcrAg, and HBV DNA levels, will be summarized (n, mean, SD, median, Q1, Q3, minimum, and maximum) by cohort and study visit along with corresponding change from baseline. Summaries (number and percentage of subjects) of HBsAg loss (defined as undetectable HBsAg measured on 2 separate, consecutive occasions, at least 2 weeks apart) will be provided by cohort and study visit.

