6.7.2. Analysis Methods

HBV viral parameters (quantitative), the raw values and the absolute change from baseline at each post-baseline visit up to Week 8 visit will be summarized descriptively (n, mean, SD, median, Q1, Q3, min, max) by VIR-3434 treatment cohort and placebo.

Similarly, the raw values and the change from baseline at nadir during the follow-up period up to Week 8 in HBsAg and HBV DNA (Part D only) will be summarized descriptively (n, mean, SD, median, Q1, Q3, min, max) by VIR-3434 treatment cohort and placebo.

In addition, mean (\pm SD) of change from baseline in HBsAg (Part B, C, and D) and HBV DNA (Part D only) will be plotted at each post-baseline visit up to Week 8 by VIR-3434 treatment cohort and placebo.

HBeAg loss, HBsAg loss, Anti-HBs seroconversion, and Anti-HBe seroconversion: the percentage and number of participants who ever met each of the variables during the follow-up period up to Week 8 will be summarized and presented by VIR-3434 treatment cohort and placebo.

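### SAP 6.7.1 can count administered VIR-3434 as anti-HBs seroconversion in active participants only, unless the assay is shown not to react with the drug

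*SAP*

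**What the plan says.** SAP 6.7.1 defines the variable as "Anti-HBs seroconversion: HBsAb changing from negative or missing at baseline to positive". Positive means at or above LLOQ at any post-baseline visit up to Week 8, and the variable applies to participants whose baseline anti-HBs is negative or missing. SAP 6.7.2 then reports "the percentage and number of participants who ever met each of the variables during the follow-up period up to Week 8", by VIR-3434 cohort and placebo.

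Protocol 2.2.1 describes the drug: "VIR-3434 is a half-life extended human monoclonal antibody that binds the antigenic loop present in all forms of the surface envelope protein". On persistence, Protocol 2.3.2 says that "terminal elimination half-life of VIR-3434 in humans was predicted to be approximately 58 days". Protocol 6.4, criterion 11, requires "Negative anti-HBs at screening" in Parts B, C and D. Placebo is normal saline (Protocol synopsis and 7.3.1).

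On the assay, Protocol 8.17 lists anti-HBs among the antiviral assessments and adds only that "Details regarding the processing and shipping of the samples are provided in the Laboratory Manual". Protocol 10.6 plans summaries of levels: "HBsAg, anti-HBs, HBeAg, anti-HBe, HBV RNA, HBcrAg, and HBV DNA levels, will be summarized". It does not name seroconversion.

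**The concern.** Anti-HBs is antibody to HBsAg, and so is the study drug. An assay that registers antibody to HBsAg whatever its source would register VIR-3434 too. Active participants could then meet the definition because they were dosed, while placebo participants, who received saline, could not.

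The label matters because of how it will be read. Protocol 2.1 gives the laboratory hallmark of chronic infection as "persistence of HBsAg in the blood for greater than 6 months and lack of detectable anti-HBs antibody", and Protocol 2.4 lists stimulation of adaptive immunity against HBV among the potential benefits. A row titled seroconversion, higher on active than on placebo, invites the conclusion that the host has begun to make antibody. At stake is the meaning of one descriptive row and of its active-versus-placebo contrast.

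**Working it through.** **1. Who can be counted.** Criterion 11 requires negative anti-HBs at screening, and SAP Appendix 2 takes screening as the anti-HBs baseline. The restriction to participants negative or missing at baseline therefore removes essentially no one, and every active participant can be counted.

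**2. How little is needed.** One positive result suffices. In the same section HBsAg loss needs two consecutive visits at least 2 weeks apart, and in SAP 6.6.1 binding ADA needs a screening and a confirmatory positive. Anti-HBs has no confirmation rule and no rule for drug in the sample.

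**3. Is drug expected at the anti-HBs visits?** The analysis visits are Weeks 1, 2, 4 and 8 (Days 8, 15, 29 and 57, or 7, 14, 28 and 56 days after dosing). First reproduce the stated half-life from the Protocol 2.3.2 inputs: CL 65.7 mL/day, V1 2.43 L, Q 612.7 mL/day, V2 2.85 L.

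- k10 = CL/V1 = 0.0657/2.43 = 0.02704 per day
- k12 = Q/V1 = 0.6127/2.43 = 0.25214 per day
- k21 = Q/V2 = 0.6127/2.85 = 0.21498 per day
- sum s = 0.49416; k10 × k21 = 0.005813
- β = [s − √(s² − 4·k10·k21)]/2 = (0.49416 − 0.47005)/2 = 0.01206 per day
- t½ = ln 2/β = 57.5 days, against the stated value of about 58

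Week 8 falls 56/57.5 = 0.97 of one terminal half-life after dosing, so the model predicts drug in serum at all four visits.

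**4. Does this carry over to patients?** The model is linear, has no target, and was used to simulate the Part A doses in healthy subjects. Participants in Parts B, C and D carry HBsAg, and persistence may be shorter. As a sensitivity check, take assumed half-lives that are not in the documents and a simple exponential decline, 0.5^(t/t½), from the starting level:

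| Assumed t½ (days) | Level 7 days after dose | Level 56 days after dose |
|---|---|---|
| 21 | 0.79 | 0.16 |
| 10 | 0.62 | 0.02 |
| 5 | 0.38 | 0.0004 |

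Drug may be nearly gone by Week 8, but an appreciable share would remain at Week 1, and one early positive is enough.

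**5. What is known of the assay.** Neither document names the anti-HBs assay, gives its LLOQ, or says whether it detects free or HBsAg-bound VIR-3434. The modifications table in SAP 6.8.1 does not mention the point.

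**6. Size.** It cannot be derived. Planned numbers at 6:2 in the nine enrolled HBV cohorts (SAP Table 2) are:

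- Part B: 4 cohorts, 24 active and 8 placebo
- Part C: 3 cohorts, 18 active and 6 placebo
- Part D: 2 cohorts, 12 active and 4 placebo

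One drug-derived positive moves an active cohort by 1/6 = 16.7 percentage points. As an illustration only, suppose there is no host response and a chance q, independent between participants, that drug is read as anti-HBs. The probability of at least one apparent seroconverter among 6 is 1 − (1 − q)^6: 0.47 for q = 0.10, 0.82 for q = 0.25, and 0.98 for q = 0.50. It is 0 if q = 0. In placebo participants it is 0 throughout.

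**The case against.** The strongest objection is that the deciding fact is an assay property that the reader cannot see. It may be settled in the Laboratory Manual or in redacted text. The assay may not react with VIR-3434, or drug bound to circulating HBsAg may be unreadable. This stands: the documents establish silence in the visible text, not that the sponsor overlooked the matter.

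It also stands that the row is not a listed primary or secondary endpoint, that SAP section 4 declares the study exploratory with no formal hypotheses, and that the SAP never uses the words host response. That reading comes from the label.

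A further objection is that the data are already available to a careful reader. SAP 6.1 lists all individual data, SAP 6.5.2 lists concentrations with actual sampling times, and Protocol 10.5 plans PK/pharmacodynamic analyses. This is only partly an answer. A listing lets someone investigate, but it does not correct a summary row that is labelled seroconversion and set against placebo.

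A reader might infer that the assay does read the drug, so that the seroconversion counts will be false. The documents do not support this, since they say nothing of the assay's reactivity. Nor does the 58-day half-life show that patients still carry drug at Week 8, because it comes from a model without target.

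**Conclusion.** The point holds in a limited, conditional form. As written, the rule can count administered drug as seroconversion in active participants only, unless the assay is shown not to react with VIR-3434. This rests on three documented facts (the drug binds HBsAg, entry requires negative anti-HBs, placebo is saline) and on the prediction that drug is in serum at one or more anti-HBs visits. The one unknown is assay reactivity. If there is none, the row is sound.

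The size is undetermined and may be zero. No test or error rate is affected. A reader might also infer that dose decisions are at risk, because the Safety Review Committee reviews antiviral data, but nothing in the documents ties a decision to this row. It is a minor matter of labelling and interpretation.

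**What to change.** In SAP 6.7.1, state whether the anti-HBs assay detects free or complexed VIR-3434.

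- If it is shown not to, keep the row and add a footnote saying so.
- If it does, or this is unknown, retitle the row *anti-HBs assay positivity (may include circulating VIR-3434)*. Show results by visit beside the VIR-3434 concentration from the same draw, and draw no host-seroconversion conclusion from it in active cohorts. Match on collection date and time, because the anti-HBs Week 1 analysis window is Days 1 to 11 while PK keeps the protocol windows (SAP Appendix 2, note 5).

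The cost is one sentence and, in the second case, a retitled row and a merge. PK is already sampled at the same visits (Protocol Appendix 3), so no new samples are needed. The visible text of Protocol 10.6 commits only to summarizing levels, so the retitle breaks no visible commitment. The downside is that few or no interpretable seroconversions may remain by Week 8.

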Urinalysis ^{n,o}	X	X			X		X							
Urine for drugs of abuse ^p	X													
Study drug administration ^q		X												
Blood samples for PK analysis ^r		X	X	X	X	X	X	X	X	X	X	X	X	X
Blood samples for immunogenicity analysis ^s		X					X	X	X	X	X	X	X	X
Blood sample for quantitative HBsAg	X	X	X	X	X	X	X	X	X	X	X	X	X	X
Blood sample for anti-HBs	X				X		X	X	X	X	X	X	X	X
Blood sample for HBeAg qualitative	X								X ^t					X ^t
Blood sample for HBeAg quantitative ^t		X						X	X					X
Blood sample for anti-HBe		X							X					X
Blood sample for HBV RNA quantitation and HBcrAg quantitation		X						X	X	X		X	X	X

Part B, C, and D															
Study Stage	Screening	Dosing Day ^a	Post-dose Follow-up Period							Extended Follow-up Period ^b					
Study Visit Week					W1		W2	W4	W8/ET ^c	W12	W16	W24	W32	W40 / EF ^d	
Study Visit Day±Visit Window	D -42 to -1	D1 ^e	D2	D4+1	D8±1	D11±1	D15±2	D29±2	D57±7	D85 ±7	D113 ±7	D169 ±7	D225 ±7	D281 ±7	
Blood sample for HBV DNA quantitation ^u	X	X	X ^v	X ^v	X	X ^v	X	X	X	X	X ^v	X	X ^v	X	
Blood sample for analysis of peripheral immune responses ^w		X			X		X	X	X	X		X		X	
Blood sample for RNA Paxgene tube ^x		X			X		X	X	X	X		X		X	
HBV resistance surveillance ^{u,y}		X			X		X	X	X	X	X	X	X	X	
Blood sample for Fc gamma receptor genotyping and for immunoglobulin allotyping		X													
CCI															
Local tolerability ^{aa}		X	X	X	X										
Review/record AEs ^{bb}	X									X					
Concomitant medications								X							
NRTI medication adherence ^{cc}								X							

AE = adverse event; ECG = electrocardiogram; EF = end of follow-up; ET = end of treatment; HBcrAg = hepatitis B core-related antigen; HBeAg = hepatitis B e-antigen; HBsAg = hepatitis B surface antigen; HBV = Hepatitis B Virus; NRTI = nucleoside/nucleotide reverse transcriptase inhibitor; PK = pharmacokinetic; SAD = single ascending dose

Note: When scheduled at the same timepoints, the assessments of vital signs and 12-lead ECGs must be performed before the blood sample collections.

- ^a Subjects may be admitted to the clinical investigative site on Day -1 or 1 and discharged after all study assessments are performed on Day 1. Patients must be monitored through at least 6 hours post-dose prior to discharge.

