6. STATISTICAL ANALYSES

6.1. General Considerations

The study assessments and time points schedule are provided in the study protocol. All individual participant data for those who were randomized to study intervention will be presented in data listings.

Continuous variables will be summarized using the following descriptive summary statistics: the number of participants (n), mean, standard deviation (SD), median, minimum value (min), and maximum value (max), unless otherwise specified.

In general, the precision of the measurement for each continuous variable will be used to determine the number of decimal places to present in tables, figures, and derived listings. Unless otherwise specified, raw data will be presented with the same number of decimals as collected, and derived data will be presented with an appropriate number of decimals based on general practice, mathematical rationale, or scientific rationale. Any values that require transformation to standard units (metric or SI) will be converted with the appropriate corresponding precision.

Categorical variables will be summarized using counts and percentages. Generally, percentages will be presented to 1 decimal place.

Baseline Value: Unless otherwise specified, the baseline value will be defined as the most recent non-missing (scheduled or unscheduled) measurement collected prior to the administration of study intervention.

If multiple measurements that are prior to dosing are recorded on the same date and with the same time or if time is not available, then the average of these measurements will be considered the baseline value.

Absolute change from baseline will be calculated as post-baseline value - baseline value.

Treatment-emergent (TE) period: Unless otherwise specified, the TE period will include the time from the administration of study drug until the Week 24 visit (or the Day 169, if the Week 24 visit is unavailable) for Part A, and the Week 8 visit (or the Day 57, if the Week 8 visit is unavailable) for Part B, C, and D.

Unscheduled visits: Unscheduled visit measurements will be included in analysis as follows:

1. In scheduled visit windows per specified visit windowing rules, if applicable
2. In the derivation of baseline and last follow-up measurements
3. In the derivation of maximum and minimum values and/or maximum and minimum change from baseline values during follow-up period or TE period
4. In individual participant data listings as appropriate

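### SAP 6.7.1 treats a missing baseline anti-HBe as negative, so a positive result by Week 8 can be reported as a seroconversion although no change was observed

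*SAP*

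**What the plan says.** SAP 6.7.1 sets the event as "Anti-HBe seroconversion: HBeAb changing from negative or missing at baseline to positive at any post-baseline visit (up to Week 8" and limits the population with the clause "which will be only applied for participants with negative or missing Anti-HBe at baseline". A missing baseline is thus accepted in both the numerator and the denominator. For this and three other response variables, SAP 6.7.2 states that "the percentage and number of participants who ever met each of the variables during the follow-up period up to Week 8 will be summarized", by VIR-3434 cohort and placebo.

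Under SAP 6.1, "the baseline value will be defined as the most recent non-missing (scheduled or unscheduled) measurement collected prior to the administration of study intervention". The same section says that missing data are in general not imputed unless otherwise specified.

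On sampling, Protocol 8.17 says that "assessment of screening viral parameters will include: HBsAg, anti-HBs, HBeAg (qualitative), and HBV DNA"; anti-HBe is not in that list. The anti-HBe row of the schedule in Protocol Appendix 3 has samples at Day 1 (pre-dose), Week 8 and Week 40 only. SAP Appendix 2 accordingly gives anti-HBe one baseline visit (Day 1) and one post-baseline visit (Week 8) in the main follow-up.

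**The concern.** Seroconversion is a change from negative to positive, and a change cannot be established without a starting value. Accepting a missing baseline imputes it as negative, and the SAP gives no reason for doing so.

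For anti-HBe nothing else in the plan supports that imputation. No scheduled screening sample exists to stand in for a lost Day 1 result. The inclusion and exclusion criteria in Protocol 6.4 and 6.5 do not ask for a negative anti-HBe. Prior positivity is plausible as well: Part B requires "Part B only: HBeAg-negative at screening", Parts C and D admit HBeAg-negative subjects, and Protocol 2.1 names HBeAg and anti-HBe together as a marker used to stage chronic infection.

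At stake is a reported count and percentage of an antiviral response in groups of four to eight subjects, where a single wrongly counted subject is visible in the table.

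**Working it through.** The documents give no anti-HBe seroconversion figure and no sample-size calculation, so there is no plan figure to reproduce. The check has two parts: whether the rule can miscount, and by how much.

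**1. Comparison with the neighbouring definitions**

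| Variable (SAP 6.7.1) | Baseline required | What protects the baseline |
|---|---|---|
| HBeAg loss | Observed positive | Missing baseline does not qualify |
| HBsAg loss | Observed positive | Missing baseline does not qualify |
| Anti-HBs seroconversion | Negative or missing | Inclusion criterion 11 requires a negative screening result, and SAP Appendix 2 uses screening as the baseline visit |
| Anti-HBe seroconversion | Negative or missing | Nothing found in either document |

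Only the anti-HBe variable combines acceptance of a missing baseline with no eligibility safeguard.

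**2. Size of one miscount**

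Inputs:
- Each cohort is 6 active to 2 placebo (Protocol Tables 2, 4, 5 and 6).
- Placebo is pooled across dose cohorts by route within each Part (Protocol synopsis, Statistical Methods).
- Enrolled cohorts number four in Part B, three in Part C and two in Part D (SAP Table 2). Placebo is therefore 4 × 2 = 8, 3 × 2 = 6 and 2 × 2 = 4 subjects.

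Let k be the number observed negative at baseline. Suppose none of them seroconverts, one further subject has a missing baseline and is positive at Week 8, and any others were already positive at baseline and so fall outside the variable. Excluding the missing-baseline subject, the rate is 0/k. Under the SAP rule it is 1/(k+1).

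| k in a six-subject active cohort | Excluding missing baseline | SAP rule |
|---|---|---|
| 5 | 0/5 | 1/6 = 16.7% |
| 4 | 0/4 | 1/5 = 20.0% |
| 3 | 0/3 | 1/4 = 25.0% |
| 2 | 0/2 | 1/3 = 33.3% |
| 1 | 0/1 | 1/2 = 50.0% |
| 0 | not estimable | 1/1 = 100% |

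For pooled placebo the smallest shift occurs when everyone else is baseline-negative: 1/8 = 12.5% in Part B, 1/6 = 16.7% in Part C and 1/4 = 25.0% in Part D.

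**3. Chance that a missing-baseline subject is miscounted**

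This depends on the baseline anti-HBe prevalence p, which the documents do not give. Assume that status persists to Week 8 and that subjects are independent. One missing-baseline subject is falsely counted with probability p, and with two the chance of at least one false count is 1 − (1 − p)².

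| Assumed p | One missing | Two missing |
|---|---|---|
| 10% | 10% | 1 − 0.9² = 19% |
| 50% | 50% | 1 − 0.5² = 75% |
| 90% | 90% | 1 − 0.1² = 99% |

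These chances are conditional on a baseline being missing. How often that happens is also not given.

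**The case against.** The strongest reply is that the rule may never operate. Day 1 pre-dose sampling takes place at the dosing visit, any unscheduled pre-dose value would serve as baseline, and SAP Appendix 2 (note 3) treats a scheduled Day 1 sample of uncertain timing as pre-dose. Neither document suggests that Day 1 results will be missing. This stands: the error is possible, not certain.

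The stakes are also low. SAP section 4 plans no hypotheses, SAP 6.3 plans no efficacy analysis, and anti-HBe seroconversion is not among the visible primary or secondary endpoints (other endpoints are redacted). The participant listings would let a careful reader find a seroconverter without a baseline. This stands too.

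A third reply is that the plan treats missing baselines this way elsewhere: treatment-induced ADA in SAP 6.6.1 and treatment-emergent laboratory abnormalities in Protocol 10.4.2. Those precedents show a deliberate convention, but there the convention errs toward reporting more harm. It does not carry over to an activity variable, where it can report a response that did not occur.

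A reader might infer that the rule favours VIR-3434. The documents do not support that. It applies equally to placebo, and in Part D the smallest possible shift is larger in pooled placebo (25.0%) than in an active cohort (16.7%). More false counts might be expected among active subjects because there are more of them, but that does not bias the rate. A missing-baseline subject who is negative at Week 8 enlarges the denominator and lowers the rate if there are true events.

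**Conclusion.** The point holds as a defect of definition in one descriptive variable. Followed exactly, SAP 6.7.1 can count a seroconversion that was not observed, and neither a screening sample nor an eligibility criterion prevents it.

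If one missing-baseline subject is positive at Week 8 and there are no true events, a six-subject active cohort shows between 16.7% and 100%. The 16.7% figure is the minimum and requires the other five subjects all to be baseline-negative; it should not be read as the typical effect. Whether the event counted is false depends on the subject's unknown earlier status.

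It would go too far to say that the rule will produce false seroconversions, or that it tilts the comparison toward the drug. The first needs a missing Day 1 result in a subject who was already positive, and neither frequency is documented; the second is not shown. The priority is low, but the correction is simple.

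**What to change.** In the anti-HBe definition in SAP 6.7.1, delete the words *or missing* from both the event clause and the denominator clause. Require a documented negative pre-dose result. In the table, report the denominator and, on a separate line, the number of subjects with a missing baseline and their Week 8 result.

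The same two deletions in the anti-HBs definition, making four in all, would keep the two consistent but change almost nothing, because eligible subjects must already have a negative screening anti-HBs.

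The cost is a short wording edit before the SAP is finalized, or a SAP amendment after approval. The denominator loses the few subjects, if any, without a baseline result; their change could not have been established in any case.
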